4.2.2.4 Tipping Point analysis

Tipping point analyses will also be implemented as a supportive analysis for the primary efficacy endpoint.

The objective of the tipping point analyses is to identify assumptions about the missing data under which the conclusions from the main analysis change (ie, under which there is no longer evidence of a treatment effect. These tipping point analyses will only be performed if the primary efficacy analysis results in a statistically significant treatment effect ($p < 0.05$).

As a first step, the worst-case scenario will be evaluated. Specifically, all BKZ-randomized subjects with a missing ACR50 at Week 16 (or non-missing ACR50 after study treatment discontinuation) will be imputed as non-responders, while all placebo-randomized subjects with a missing ACR50 at Week 16 will be imputed as responders. While there is little justification for such an approach, it makes the most putative assumption possible against a BKZ treatment effect. After applying this imputation approach, a logistic regression model consistent with the

one described for the primary analysis will be applied. If the p-value for the odds ratio of BKZ versus placebo is less than 0.05, then no further tipping point analyses are needed.

If this analysis based on the worst-case scenario results in a p-value greater than 0.05, then additional tipping point analyses will be performed. In practice, it implies different delta adjustments will be made to the assumed responses on the missing data (where missing values include observations after the intercurrent event date and any other missing values) in each treatment group independently with various degrees of plausibility with the goal to find for each treatment group the “tipping point” that will significantly reverse the primary result which yielded a p-value less than 0.05. These delta adjustments will be done on each component of ACR50 as follows:

- **Step 1:** The same MCMC method described in [Section 4.2.2.2](#) will be implemented for non-monotone (intermittent) missing pattern values, using the same imputation model. This will be based on 100 imputations.
- **Step 2:** Based on the dataset obtained in Step 1, a monotone regression model will be applied (using the same imputation model as in Step 1) and as described in [Section 4.2.2.2](#) . This will be based on 1 imputation.
- **Step 3:** Imputed values will be shifted using a delta adjustment independently in each treatment group.

Once defined, the same delta adjustment value will be applied on the imputed values for the Week 16 visit only. The selected scenario will assume that subjects randomized to BKZ and who have missing data have a lower probability of response compared to subjects randomized to placebo with missing data.

- For ACR components for which high scores are associated with a less favorable outcome, it will mean that:
 - A positive shift is applied to the imputed value for subjects randomized to BKZ in order to increase the imputed value.
 - A negative shift is applied to the imputed value for subjects randomized to placebo in order to decrease the imputed value.

A set of possible values will be first pre-defined for the delta parameter as follows:

- For all ACR components, the value of the initial delta parameter will be equivalent to a specific percentage of the possible range of each component (ie, 5%). For hs-CRP, the range will be based on the log-transformed values at Week 16. The delta parameters for each endpoint are listed in the [Table 7-3](#) .

Table 7-3: Tipping point analysis: Delta parameter for each ACR component

ACR component ¹	Range	Delta
SJC	0-66	3.3
TJC	0-68	3.4
HAQ-DI	0-3	0.15
PtAAP, PhGA-PsA, PGA-PsA	0-100	5

ACR component ¹	Range	Delta
hs-CRP ²	Observed range of the log _e transformed values for all subjects at Week 16	5% of the observed range

¹The shifted imputed value should not exceed the range for the ACR component.

²The delta adjustment will be applied on the log_e transformed imputed and observed values which will then be exponentiated prior to deriving endpoint.

- **Step 4:** Standard rounding rules will be applied to the imputed values. If the SAS® PROC MI yields a value outside of the range for the given component, the value will be updated after the imputation has been performed to be within the predefined range.
- **Step 5:** Repeat steps 1 to 4 for each ACR component. The composite binary endpoint (ACR50) will then be derived based on the multiple shifted imputed data sets obtained for each component.
- **Step 6:** Additionally, as the primary endpoint is derived using NRI, subjects randomized to BKZ with missing data (where missing values include observations after the IE date and any other missing values) should be set to non-response, after applying the delta adjustment outlined in Step 3 above. This ensures subjects randomized to BKZ do not have a higher probability of response in the tipping point analyses compared to the primary analysis (ie, a subject randomized to BKZ who is non-responder in the primary analysis cannot become a responder in the tipping point analyses).
- **Step 7:** In the data obtained, for each value of the imputation number, ACR50 will be analyzed using a logistic regression model with factors of treatment group, region, and prior TNFα inhibitor exposure at Baseline as fixed effects.
- **Step 8:** The results obtained from the 100 logistic regression analyses in Step 6 will be combined for overall inference using Rubin's rules, and the results obtained for each shift parameter will be presented in a single table.
- **Step 9:** Step 3 to Step 8 will be repeated so that, at each iteration, missing values are adjusted with a larger shift than at the previous iteration. Depending on the results obtained, delta parameters with more granularity (eg, 2 times, 3 times the initial delta) will be investigated. The process will go on until the p-value for the odds ratio between BKZ and placebo is no longer statistically significant (ie, ≥ 0.05). The odds ratio, 95% CI, and p-values obtained for each value of delta will be combined in one single table.

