2.4 Determination of sample size

Approximately 390 subjects will be randomly assigned in a 2:1 ratio to the following treatment groups: BKZ 160mg sc Q4W (260 subjects) and placebo (130 subjects).

The primary efficacy analysis is based on the primary comparison of BKZ versus placebo for ACR50 response at Week 16.

All sample size and power calculations were done at a significance level of 0.05.

All sample size and power calculations were performed using the software nQuery Advisor® 7.0.

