2.4.1 Power calculation for primary endpoint

The sample size assumptions for BKZ vs placebo are based on the ACR50 response data in the subgroup of TNF α -IR patients from the Phase 2b BKZ study in a mixed prior TNF α therapy

population of subjects with moderate-to-severe PsA (PA0008). Sample size calculations for a TNF α -IR population are also based on ACR50 responses at Week 16 in the SPIRIT-P2 study.

Observed ACR50 at Week 12 results in the PA0008 TNF α -IR populations were in a small number of subjects; BKZ 160mg (n=7), 320mg (n=8), and 320mg (initial dose) plus 160mg (n=8) and ranged from 14.3% to 37.5%.

The ixekizumab Phase 3 study SPIRIT-P2 is conducted on a similar patient population to that in this study and showed a 35% (n=122) ACR50 response at Week 16. Therefore, taking into account the range of ACR50 responses at Week 12 in PA0008, the estimated ACR50 response at Week 16 in the BKZ 160mg sc Q4W group is conservatively assumed to be 26%.

For placebo, a similar approach as above is used. In the PA0008 TNF α -IR population, an ACR50 response of 11.1% (n=9) was observed at Week 12. The observed placebo ACR50 response at Week 16 was less than 10% in the SPIRIT-P2 study (n=118). Therefore, the estimated ACR50 response at Week 16 in the placebo group is assumed to be 10%.

The sample size for showing statistical superiority of BKZ vs placebo was calculated using a 2-sided 2-sample Chi-square test with continuity correction (Fleiss et al, 1980). Assuming 260 subjects in the BKZ group and 130 subjects in the placebo group, the test for detecting statistical superiority of BKZ 160mg vs placebo based on ACR50 response at Week 16 has 96% power to detect a true treatment difference of 16% (odds ratio (OR) of 3.16).

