8.1.4.7 Tipping point analysis

The degree of the departure from the MAR assumption to overturn conclusions from the primary analysis will be investigated in a tipping point analysis. This analysis will be performed on the monotone missing data and only if the primary analysis is significant at $\alpha=0.05$. Intermittent missing data will be imputed using the MCMC method. In this analysis, it will be assumed that subjects who have missing data and are randomized to BKZ have a lower probability of response compared to subjects who have missing data and are randomized to placebo.

The analysis will be primarily conducted on the binary response endpoint itself in considering the worst-case scenario that subjects who have missing ACR50 response will be set as non-responders if they are randomized to BKZ, and as responders if they are randomized to Placebo. If the result tips, then the tipping point analysis will be reconducted on the ACR50 endpoint after having delta-adjusted each individual component of the ACR50 endpoint. For both analyses, the same model as used for the primary efficacy analysis will be conducted on the RS. If the delta parameter value for which the study conclusion under MAR is reversed is plausible, the conclusion under MAR will then be questionable.

Refer to [Section 4.2.2.4](#) for more details on the methodology.

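### Three rules of the ACR50 tipping-point analysis need correcting: the hs-CRP shift reaches observed data, the worst-case screen is not the worst case, and shifting imputed BKZ values has no effect

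*SAP*

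**What the plan says.** SAP Section 4.2.2.4 describes a two-stage supportive analysis, run only if the primary ACR50 result is significant.

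- **Worst-case screen.** BKZ subjects whose Week 16 ACR50 is missing, or is observed after they stopped treatment, become non-responders, "while all placebo-randomized subjects with a missing ACR50 at Week 16 will be imputed as responders". The SAP presents this as the most adverse assumption available. If the odds ratio still has p<0.05, nothing further is done.
- **Delta stage.** The aim is a tipping point for each treatment group, and data after the intercurrent event count as missing in both arms. Step 3: "Imputed values will be shifted using a delta adjustment independently in each treatment group". BKZ values are moved up (worse) and placebo values down (better), at Week 16 only.
- **Delta table, footnote 2.** For hs-CRP the delta is 5% of the observed log range, and the footnote applies it to observed as well as imputed values.
- **Step 6.** BKZ subjects with missing data, including post-event observations, "should be set to non-response, after applying the delta adjustment outlined in Step 3 above". The stated reason is that a BKZ non-responder in the primary analysis must not become a responder here.

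Section 8.1.4.7 gives the purpose: "The degree of the departure from the MAR assumption to overturn conclusions from the primary analysis will be investigated".

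**The concern.** A tipping-point analysis should change only what is assumed about unobserved (or deliberately discarded) outcomes, and should show how far those assumptions must move before the conclusion fails. Each of the three rules departs from that.

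If observed CRP is shifted, the result can tip for a reason unrelated to missing data. If the screen is milder than the worst case, the analysis can stop when the true worst case is not significant. If the BKZ delta cannot alter any BKZ response, the results table will list BKZ deltas that did nothing, and a reader may take them as evidence of robustness on the BKZ side.

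**Working it through.** **1. The plan's own figures.** The table deltas are 5% of each range: 0.05×66 = 3.3, 0.05×68 = 3.4, 0.05×3 = 0.15, 0.05×100 = 5. All match. For power (Section 2.4.1), the inputs are 260 v 130 subjects, 26% v 10%, two-sided 0.05.
- Odds ratio = (0.26/0.74)/(0.10/0.90) = 3.16, as stated.
- Fleiss correction, with r = 2, Δ = 0.16 and n the uncorrected placebo group size: n_c = (n/4)·[1+√(1+2(r+1)/(n·r·Δ))]². Setting n_c = 130 gives n = 120.8.
- Power is 96.6% with the correction (97.6% without), against the stated 96%. The sample size is not in question, and the same rates are used in step 4.

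**2. Step 3 against Step 6.** Step 3 shifts imputed values. The BKZ subjects who have imputed values are those with missing or post-event data, and Step 6 sets these to non-response whatever the shift. A partly missing record offers no way round this: under Section 8.1.1, where ACR50 can be derived from observed components, imputed values do not change it. An illustrative simulation (400 trials, 8% missing and component distributions assumed, hs-CRP log range taken within arm rather than pooled) gives these mean BKZ responders out of 260:

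| Multiple of delta | 0 | 1 | 3 | 10 |
|---|---|---|---|---|
| Without Step 6 | 55.6 | 51.6 | 51.2 | 51.2 |
| With Step 6, imputed values shifted only | 51.2 | 51.2 | 51.2 | 51.2 |
| With Step 6, observed hs-CRP also shifted | 51.2 | 46.7 | 42.4 | 42.0 |

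The second row is flat. In the third row the whole fall is among fully observed subjects, whom Step 6 does not touch.

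**3. Size of the hs-CRP shift.** The Week 16 maximum is not known in advance, so 50 to 200 mg/L is assumed. The minimum is taken as half the LLOQ, 0.05 mg/L. Factor per delta = exp{0.05·[ln(max) − ln(0.05)]}:
- max 50: exp(0.05×6.91) = 1.41
- max 100: exp(0.05×7.60) = 1.46
- max 200: exp(0.05×8.29) = 1.51

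At a maximum of 100 mg/L, an observed 60% fall on BKZ becomes 1 − 0.40×1.46 ≈ 42%, so the 50% criterion is lost. An observed 30% fall on placebo becomes 1 − 0.70/1.46 ≈ 52%, so it is gained. ACR50 changes only if hs-CRP is the deciding third of the five measures and both joint counts have improved.

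**4. The worst-case screen.** At the planning rates, responders are 0.26×260 ≈ 68 and 0.10×130 = 13. Use an unadjusted Wald test, z = ln(OR)/√(1/a+1/b+1/c+1/d), where a and b are BKZ responders and non-responders and c and d the same for placebo:
- 9 added placebo responders (22/130): OR = (68/192)/(22/108) = 1.74, SE = 0.273, z = 2.02, p = 0.043. The analysis stops.
- 10 added (23/130): OR = (68/192)/(23/107) = 1.65, SE = 0.270, z = 1.85, p = 0.064. The analysis continues.

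Near that boundary, one placebo subject with an observed post-discontinuation ACR50 decides whether the delta stage is run.

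**The case against.** **Step 6 is deliberate and explained.** It holds BKZ subjects with missing data at their most adverse value while the placebo delta grows. This stands. A reader might infer that Step 6 undoes the whole analysis; it does not, because the placebo search still works and is conservative. Nor does Step 6 cancel every BKZ shift: under a literal footnote 2, the shift of observed BKZ hs-CRP survives it.

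**Footnote 2 may mean only that all CRP values are log-transformed and back-transformed.** Step 3, the paragraph following it and footnote 1 all speak of imputed values. That is probably the intention, but the sentence attaches the delta itself to observed values, and a programmer could follow it. The error works against BKZ, so it would not give false reassurance.

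**The asymmetric screen may be loose drafting.** Section 8.1.4.7 states the rule symmetrically for missing responses. The affected group is also small: because discontinuation is dated 31 days after treatment end (Section 3.4), a subject dosed on schedule at Week 12 has not discontinued by Week 16. Both points limit the size. However, the post-discontinuation clause is written for BKZ only, subjects who stop treatment are encouraged to keep attending visits, and the screen can end the analysis.

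**This is not the only look beyond MAR.** A reader might infer that it is. The primary non-responder rule is not a MAR analysis, and reference-based imputation is applied to the individual ACR components (Section 8.1.4.4). What can be said is that this is the only delta-based analysis of ACR50 itself.

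**Conclusion.** The point holds as three errors of specification in one supportive analysis. The primary test, its power and the testing hierarchy are untouched.

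- **hs-CRP footnote:** contradicts Step 3. Followed literally, it alters observed CRP by a factor of about 1.4 to 1.5 per delta. This rests on the assumed maximum of 50 to 200 mg/L, and its effect on ACR50 is confined to subjects for whom hs-CRP decides the 3-of-5 rule.
- **Worst-case screen:** not the most adverse case as written. The 9-versus-10 threshold shows that a wrong stop is possible, not that it is likely. It uses planning rates and omits the model's adjustment for region and prior TNFα inhibitor exposure.
- **BKZ shifts:** with Step 6 in place, shifting imputed BKZ values has no effect at any multiple. The per-group tipping point cannot be delivered; a placebo-side search can.

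These should be corrected before unblinding.

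**What to change.** 1. In footnote 2 of the delta table, delete the reference to observed values. Observed hs-CRP may be log-transformed and back-transformed, but not shifted.
2. In the worst-case screen (Sections 4.2.2.4 and 8.1.4.7), also set placebo subjects with observed data after discontinuation to responders, mirroring the BKZ rule.
3. Keep Step 6, delete the BKZ shifts, and describe the analysis as a placebo-arm tipping point with BKZ subjects who have missing or post-event data fixed at non-response. Amend the statement of aim to match.

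Dropping Step 6 in favour of a two-way grid of deltas starting from MAR is possible but is a trade-off: BKZ responders would start above the primary-analysis count (55.6 against 51.2 in the illustration), which Step 6 was written to prevent.

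The cost is SAP wording, minor programming, and a screen that is slightly harder to pass.

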4.2.2.5 Treatment Policy Strategy

Another supportive analysis will be performed on the primary efficacy endpoint to address intercurrent events.

The treatment policy strategy will include all available data observed at the week of interest (Week 16) regardless of the occurrence of intercurrent events. This means the analysis includes on- and off-treatment values collected after subjects prematurely discontinued study treatment but agreed to remain on the study and continued to attend visits and provide assessments at those visits. Those observed values will be analyzed according to the subject's randomized treatment. Subjects for whom efficacy data cannot be obtained at the week of interest, despite attempts to

retain them in the study, will have their data imputed using MI-MCMC/monotone regression (Section 4.2.2.2).

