4.2.2.2 Composite binary endpoints

For composite binary endpoints, the MI method will be applied as follows:

- **Step 1:** The MCMC/monotone regression approach described above in Step 1 for non-composite binary endpoints will be performed separately for each individual component variable.

- **Step 2:** The same rounding rules described in Step 2 above for non-composite binary endpoints will be performed for each component.
- **Step 3:** Based on the multiple imputed data sets obtained for each component, the binary response will be derived as follows:
 - The dataset obtained for each component will be merged by imputation number and subject number
 - On the dataset obtained, the binary endpoint will be derived for each subject/visit based on the component values.
 - If subjects have an IE, then the endpoint at all subsequent visits (from the day after the intercurrent event date, whether the data were observed or not) will be set to “non-response”.
- **Steps 4 and 5:** Same as Steps 4 and 5 above for non-composite binary endpoints ([Section 4.2.2.2.1](#)).

For the primary endpoint, the ‘burn-in’ option in SAS® PROC MI may be set higher than the default value. The goodness-of-fit tests to assess convergence of the MCMC will be provided in a SAS® output.

4.2.2.2.3 Calculation of adjusted responder rates, odds ratio and CIs for binary endpoints.

Estimates of the adjusted responder rates for each treatment group and the associated standard errors are obtained from the logistic regression in Step 5 on the logit scale and as such are assumed to follow a normal distribution. These estimates will be combined using Rubin’s rules and the combined estimates and associated SEs will be used to construct 95% CIs on the logit scale. The combined estimates and 95% CIs on the logit scale will be back transformed using the inverse logit link function to obtain the adjusted responder rates (%) and associated 95% CIs.

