4.2.2.3 MI – MCMC/Reference-Based imputation

For the primary analysis of the secondary continuous efficacy variable included in the testing hierarchy and the individual components of the ACR response, the Reference-Based multiple imputation method will be used. In this imputation method, the missing data will be imputed based on data from the placebo group only (Mallinckrodt, 2013).

Reference-Based MI assumes that the statistical behavior of the BKZ and placebo-treated subjects after discontinuing study medication becomes that of the placebo-treated subjects. All time points after study treatment discontinuation for BKZ and placebo groups will be considered missing. MIs are used to replace missing outcomes for BKZ- and placebo-treated subjects who discontinued using multiple draws from the posterior predictive distribution estimated from the placebo arm.

Note: SAS 9.4 may be used for this analysis where equivalent steps to those outlined below will be used to perform the imputation.

In the case of continuous endpoints, the procedure will be implemented as follows on the raw values:

1. Data will be processed sequentially, one timepoint (visit) at a time, by repeatedly calling SAS[®] PROC MI to impute missing outcome data at visits $t=1, \dots, \text{Week 16}$ (Week 16 being the time point of interest) using data from the placebo-treated subjects arm only.
 - a. *Initialization.* Set $t=1$ (Baseline visit). Create a dataset combining all records from all subjects with columns for covariates (prior TNF α exposure and region) and outcome at Baseline. Impute missing values at Baseline using prior TNF α exposure at Baseline and region.
 - b. *Iteration.* Set $t=t+1$. Create a dataset combining records from BKZ- (subjects with missing data at visit t) and all placebo-treated subjects with columns for covariates (prior TNF α exposure and region) and outcomes at visits 1 to t . In this dataset, outcomes for BKZ-randomized subjects are missing at visit t and observed or previously imputed at visits 1 to $t-1$. Outcomes for placebo-treated subjects are observed or missing at visit t and observed or previously imputed at visits 1 to $t-1$. The outcomes should be sorted in chronological order in the model.

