8.1.4.5 Analyses using treatment policy strategy imputation for missing data

The treatment policy strategy for addressing the intercurrent events will be considered. In this analysis, all available data at Week 16 will be considered regardless of the occurrence of intercurrent events. This analysis will use the same models specified for the primary analyses where subjects are analyzed according to their randomized treatment, even if they discontinued study treatment for any reason prior to Week 16 and were no longer on the randomized study treatment when the assessment was performed at Week 16.

In the context of this analysis, in addition to the statistics provided in the context of MI, the number of observed ACR50 responses regardless of the existence of IE will be also reported.

The following 4 attributes describe the treatment policy strategy analysis is detailed below:

- Population = Subjects enrolled according to the protocol-specified inclusion/exclusion criteria and randomized to IMP
- Subject-level outcome = ACR50 at Week 16
- Intercurrent event handling = Discontinuation of study medication for any reason will be handled by using the data as observed irrespective of the intercurrent event occurring.

- Population-level summary measure = Conditional odds ratio comparing ‘BKZ and other medication as needed’ to ‘placebo and other medication as needed’.

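### The treatment policy analysis of ACR50 imputes subjects who stopped treatment and were lost as if they had stayed on it

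*SAP*

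**What the plan says.** SAP 8.1.4.5 states that discontinuation of study medication is to be "handled by using the data as observed irrespective of the intercurrent event occurring". Section 3.7 makes the matching exception: off-treatment data are otherwise only listed, but they enter this analysis. Under 4.2.2.5, subjects whose Week 16 data cannot be obtained despite attempts to "retain them in the study, will have their data imputed using MI-MCMC/monotone regression" are handled by the method of 4.2.2.2.

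Section 4.2.2.2 says that this method assumes data missing at random. It is run separately for each treatment group, on the randomization strata plus the Baseline and post-Baseline values. No variable marks whether a subject has stopped treatment.

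For composite binary endpoints such as ACR50, Step 3 of the same method adds that if a subject has an intercurrent event, "then the endpoint at all subsequent visits (from the day after the intercurrent event date, whether the data were observed or not") is set to non-response. Section 8.1.1 has a similar rule for the MI analysis: visits after discontinuation are imputed even where observed.

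Section 4.2.2.3 offers another method: "Reference-Based MI assumes that the statistical behavior of the BKZ and placebo-treated subjects after discontinuing study medication becomes that of the placebo-treated subjects". It is assigned to the continuous endpoints in the hierarchy and to the ACR components.

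**The concern.** A treatment policy analysis asks how subjects did at Week 16 whether or not they stayed on drug. For those who stopped and then left, that outcome is off treatment and unobserved. A model fitted within the BKZ arm, mostly to subjects still receiving BKZ and blind to stopping, draws their values from on-treatment experience. That answers a hypothetical question inside an analysis labelled treatment policy. If benefit fades after stopping, the BKZ response rate comes out too high.

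The missing-data table in 4.2.1.6 shows only one treatment policy analysis, and 8.1.4 plots it beside the primary result. A reader will take it as the check on what happens regardless of discontinuation.

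There is also a drafting gap. Because 4.2.2.5 cites 4.2.2.2 without exception, a programmer could apply Step 3 and overwrite the off-treatment data that this analysis is meant to use.

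**Working it through.** **What the imputation represents.** Section 8.1.4.4 names two strategies for ACR component data after discontinuation. Strategy (a), ordinary MI, stands for subjects having completed their randomized treatment to Week 16. Strategy (b) is reference-based. The method cited in 4.2.2.5 is the ordinary MI of (a). By the SAP's own description, then, lost discontinuers are imputed under a hypothetical assumption.

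**Inputs, SAP 2.4 and 2.4.1.** Two-sided 0.05; 260 BKZ and 130 placebo subjects; a "2-sided 2-sample Chi-square test with continuity correction"; BKZ response that "is conservatively assumed to be 26" percent; placebo 10%.

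**The plan's own figures.** Let k = 2, d = 0.16 and p̄ = (0.10 + 2 × 0.26)/3 = 0.207. The uncorrected placebo-group size is

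n' = [z(0.975)√(p̄(1−p̄)(1+1/k)) + z(power)√(0.10×0.90 + 0.26×0.74/k)]² / d²

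and the corrected size is n = (n'/4)[1 + √(1 + 2(1+1/k)/(n'd))]². Solving for power at n = 130 gives 96.6%, against 96% stated. The odds ratio is (0.26/0.74)/(0.10/0.90) = 3.16, as stated. These figures are not in dispute; they only fix the rates used below.

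**Size of the mismatch.** Let L be the share of each arm that stopped and was lost. The SAP gives no such rate, so L is an assumption. All other subjects respond at 26% and 10%. Within-arm imputation at the arm's own rate leaves the difference at 16.0 points for every L. If lost BKZ subjects in truth respond like placebo, the BKZ rate is (1−L) × 26% + L × 10%. The placebo arm does not change. The overstatement is L × (26 − 10) points.

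| L | BKZ rate if placebo-like | Difference (points) | Overstatement (points) | Odds ratio |
|---|---|---|---|---|
| 2% | 25.7% | 15.7 | 0.3 | 3.11 |
| 5% | 25.2% | 15.2 | 0.8 | 3.03 |
| 10% | 24.4% | 14.4 | 1.6 | 2.90 |
| 15% | 23.6% | 13.6 | 2.4 | 2.78 |

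**Does such a model really impute on-treatment values?** An illustrative simulation of one arm assumed an on-treatment Week 16 mean of 36 and an off-treatment mean of about 12, with 5–10% lost and 0–5% retained off treatment. Sequential regression without a discontinuation term imputed means of 34.6 to 36.1 for lost subjects whose true means were 11.5 to 12.4. Stopping was unrelated to earlier outcomes in this simulation, so earlier visits gave no warning; this is the unfavourable case.

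**The Step 3 reading.** If every lost subject became a non-responder in both arms, the difference would be (1−L) × 16: 15.2, 14.4 and 13.6 points at 5%, 10% and 15%, with odds ratios 3.12, 3.09 and 3.05. The missing-at-random draws would be overwritten and their bias would disappear. The two problems cannot both operate on the same subjects.

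**The case against.** Several objections have force.

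- A reader might infer that the analysis does not estimate treatment policy at all. The documents do not support that. Observed Week 16 data are used on or off treatment, section 2.3 has subjects who stop IMP return for visits through Week 16, and within-arm imputation is reasonable for subjects missing while still on treatment. Only those both discontinued and lost are affected.
- Step 3 probably would not be applied. Section 4.2.2.2 disclaims the handling of intercurrent events and defers to 4.2.1; 4.2.1.3 points to 4.2.2.5; and 3.7, 4.2.2.5 and 8.1.4.5 all call for observed data. This stands: what remains is a missing clarifying sentence.
- One might also read 4.2.2.3 as contradicting 4.2.2.5. It does not. It serves a different estimand, and 4.2.1.3 says the supportive analyses deliberately assume different missing-data mechanisms.
- Immediate placebo-like response is extreme. Section 10.1.1 equates 140 days with five half-lives, so one is 28 days. A subject last dosed at Week 8 is 56 days, or two half-lives, past that dose at Week 16. The model also conditions on earlier visits, which the arithmetic ignores. Both reduce the bias.
- Harsher assumptions are already covered by the primary non-responder analysis and the worst-case step of the tipping point analysis (4.2.2.4). No hypothesis test depends on this analysis.

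None of this answers the narrow point: for lost discontinuers, the imputation is the one the SAP elsewhere describes as hypothetical.

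**Conclusion.** The point holds for one subset: subjects who discontinued IMP and have no Week 16 data. For them the imputation does not match the treatment policy estimand, and it tends to favour BKZ if benefit fades after stopping.

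The size rests on three assumptions: a loss rate the SAP does not state, the planning rates of 26% and 10%, and full reversion to placebo-like response. On these, the overstatement is 5%, 10% or 15% of the assumed 16-point effect at 5%, 10% or 15% lost. With residual drug effect and conditioning on earlier visits it would be smaller, so these figures are close to an upper bound.

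The unqualified reference to 4.2.2.2 is a separate drafting conflict and must not be added to this bias. The primary analysis and the tipping point analysis are unaffected. The change is worth making because it is cheap and makes the analysis fit its label.

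**What to change.** In 4.2.2.5 and 8.1.4.5, state that:

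1. The Step 3 non-response rule of 4.2.2.2, and the rule in 8.1.1 that imputes visits after discontinuation, do not apply to this analysis.
2. All ACR component values observed after discontinuation are kept.
3. Component values missing after an intercurrent event are imputed from retrieved dropouts, that is, subjects who stopped treatment but were still assessed. If these are too few, use the reference-based algorithm of 4.2.2.3, run afresh with observed off-treatment values retained. Set the minimum number before unblinding.
4. Values missing without an intercurrent event stay with within-arm MI-MCMC/monotone regression.

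The imputed datasets from 8.1.4.4(b) cannot be re-used, because that analysis resets observed post-discontinuation values to missing. The fallback in item 3 also rests on an untestable assumption, since it models placebo subjects rather than BKZ followed by other medication; that is why retrieved dropouts come first.

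The cost is a few sentences, one additional imputation run, and a supportive estimate likely to be slightly less favourable to BKZ.
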